2.3.4 Secondary Safety Endpoint Analysis

The secondary safety endpoint evaluates the 12-month Aveir atrial LP related CFR_A based on the CEC adjudication of adverse events. The secondary safety endpoint will be tested if all the primary endpoints are met.

An atrial LP complication is defined as an atrial device- or procedure-related SADE, including those that prevent initial LP implantation. Complications that are exclusively related to the ventricular LP or its delivery/retrieval will not be considered atrial LP complications and will be excluded from this evaluation. Complications that cannot be exclusively determined to be related to the ventricular or atrial LP will be considered atrial LP complications (e.g. femoral access complications, embolism, etc.). The secondary safety endpoint hypothesis is:

H₀: CFR_A ≤ 82% vs. H₁: CFR_A > 82%

where 82% is the PG.

The CFR_A at 12 months will be calculated using the Kaplan-Meier survival analysis. The associated one-sided lower 97.5% confidence interval will also be provided (using the Greenwood variance estimates). The null hypothesis is rejected at the 2.5% significance level if the LCB exceeds the PG of 82%. The p-value from the one-sided Z-test will be calculated and compared to the 2.5% significance level.

The secondary safety endpoint analysis will be based on the subjects in the full analysis population.

To eliminate the possible impact of Covid-19 on the confirmatory safety endpoint analysis, CEC adjudicated primary safety events (SADEs) that are related or possibly related to Covid-19 will be excluded. Subjects who have these events will be censored at the time of the event. Additional analysis with these events included will also be provided.

Statistical Analysis Plan

2.3.5 Secondary Effectiveness Endpoint Analysis

The secondary effectiveness endpoint includes evaluation of CAEP exercise protocol for atrial LP. The secondary effectiveness endpoint will be tested if all the primary endpoints are met and the secondary Safety endpoint is also met.

The secondary effectiveness CAEP endpoint hypothesis is:

H_0 : Mean Slope < 0.65 or Mean Slope > 1.35

H_1 : $0.65 \leq \text{Mean Slope} \leq 1.35$.

CAEP exercise protocol

All capable subjects who have completed the 6-minute walk test (6MWT) will be asked to perform a maximal effort CAEP exercise protocol to demonstrate an appropriate and proportional response of sensor-indicated rate in graded exercise tests. Subjects will undergo the CAEP exercise test any time after the beginning of their 3-month visit window and before the end of 6-month visit window. Each subject will undergo this test at a single visit.

Data from subjects who have completed the 6MWT and have completed at least stage 3 of the CAEP exercise protocol, or 3.6 metabolic equivalent of task (METs), will be included in the analysis. Any CAEP assessments performed which substantially deviate from the CAEP exercise protocol or where insufficient data is available will be excluded from the analysis. The results of subjects who did not meet the analysis criteria will still be reported.

A mixed effects model for repeated measures will be used to estimate the mean slope (through origin) and standard error of mean slope across N subjects.

A 95% confidence interval for the mean slope will be provided and if this interval falls within the equivalence bounds of [0.65, 1.35], the null hypothesis is rejected.

[REDACTED]

[REDACTED]

[REDACTED]

Statistical Analysis Plan

2.4 Sample Size Calculations

[REDACTED]

Sample size calculation for the primary safety endpoint at 12 months (CFR):

[REDACTED] 300 subjects [REDACTED] will provide [REDACTED] to meet a performance goal of 76.5% and reject the null hypothesis at a 2.5% one-sided significance level. [REDACTED]

Power calculation for the primary effectiveness endpoint #1 at 12 months (Rate_{EP})

[REDACTED] 240 subjects [REDACTED] to meet a performance goal of 80% and reject the null hypothesis at a 2.5% one-sided significance level. [REDACTED]

Power calculation for the primary effectiveness endpoint #2 at 3 months (Rate_{AV})

[REDACTED] 267 evaluable subjects [REDACTED] to meet a performance goal of 83% and reject the null hypothesis at a 2.5% one-sided significance level. [REDACTED]

Power calculation for the secondary safety endpoint at 12 months (CFR_A)

[REDACTED] 300 subjects [REDACTED] to meet a performance goal of 82% and reject the null hypothesis at a 2.5% one-sided significance level. [REDACTED]

Additional sample size for the study

[REDACTED] up to 200 additional de novo subjects will be enrolled [REDACTED]. Up to 50 subjects will also be enrolled to assess the upgradeability to a Aveir DR LP system in subjects previously implanted with the Aveir VR LP single chamber analysis.

[REDACTED]

2.5 Interim Analysis

[REDACTED]

Statistical Analysis Plan

[REDACTED]

2.6 Timing of Analysis

[REDACTED]

2.7 Study/Trial Success

[REDACTED]

2.8 Handling of Missing Data

A subject may discontinue from the study prior to the 12-month visit. If this situation occurs, reasons for missing data will be summarized to assess the plausibility if the missing data could affect subject's endpoint results.

In addition, sensitivity analyses will be performed to evaluate the potential impact of missing data on the primary safety and effectiveness endpoints.

Sensitivity Analyses for Primary Safety Endpoint

For the primary safety endpoint, tipping point sensitivity analysis will be conducted on all the subjects in the full analysis population.

The tipping point analysis will be performed to assess the impact of the missing data. [REDACTED]

[REDACTED]

Sensitivity Analyses for Primary Effectiveness Endpoint #1

The following sensitivity analysis will be conducted for the primary effectiveness endpoint #1.

1. Complete Case: Complete case sensitivity analysis will be conducted for subjects in the full analysis population [REDACTED]

[REDACTED]

Statistical Analysis Plan

2. Tipping Point: Tipping Point sensitivity analysis will be conducted for subjects in the full analysis population [REDACTED]

Sensitivity Analyses for Primary Effectiveness Endpoint #2

For the primary effectiveness endpoint #2, tipping point sensitivity analyses will be conducted for subjects in the full analysis population, excluding those that had an unsuccessful implant due to reasons other than AV synchrony (e.g., cardiac anatomy). For the tipping point analysis, subjects with missing data for the primary effectiveness endpoint #2 will be evaluated with respect to the success rate among these subjects. Subjects with unsuccessful implant solely due to a failure to establish i2i communication at end of implant procedure will be included and imputed as failures. Tipping point is at which the study conclusion will be altered.

2.9 Poolability Issue (if applicable)

Poolability of the primary safety endpoint and the two primary effectiveness endpoints on subjects in the full analysis population will be evaluated by region and across sites. Analysis will be performed based on available data.

The study will be conducted in up to 85 sites in the United States, Canada, Europe and Asia Pacific. The study will be conducted following the same investigational plan, monitoring plan and training plan in all regions. The consistency of results for the primary safety and effectiveness endpoints will be evaluated across regions i.e. US and OUS (outside the US) if there is a sufficient sample size in each region, and across sites with the following site categories:

Large sites: # of subjects enrolled ≥ 10

Medium sites: $4 \leq$ # of subjects enrolled ≤ 9

Small sites: # of subjects enrolled ≤ 3

Descriptive summaries for the primary safety and the two primary effectiveness endpoints will be presented across (1) Regions: US or OUS (outside the US) and (2) Site Categories (Large, Medium or Small). Consistency of results will be examined using Fisher's exact test and assessed at a significance level of 0.15. [REDACTED]

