6.2.9 Subjects without any LPs implanted

Investigators will follow subjects who leave an attempted *de novo* implant procedure without any implanted Aveir LPs for a period of at least 30 days to evaluate for adverse events. At the end of the 30 days, the investigator will withdraw the subject.

The investigator must document the nature of and reasons for the unsuccessful implant on the Implant Form. Subjects who have an unsuccessful implant will not be eligible for re-implantation attempts of any Aveir LPs at a later date during the study period.

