2.2.3 Survival Analyses

For time-to-event variables, Kaplan-Meier analysis will be conducted. Subjects without events will be censored at their last known event-free time point, and for subjects with events the time to the first event will be used for the analysis. Survival estimates of the data and associated 95% confidence interval will be presented using cumulative survival and its estimated standard error (Greenwood's formula).

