2.3.1 Primary Safety Endpoint Analysis

The primary safety endpoint evaluates the 12-month Aveir DR LP system CFR based on CEC adjudication of adverse events. A complication is defined as a device-or procedure-related serious adverse event (SADE), including those that prevent initial implantation (includes both Atrial LP and Ventricular LP complications and implant procedure-related complications).

The primary safety endpoint hypothesis is:

$H_0: CFR \leq 76.5\%$ vs. $H_1: CFR > 76.5\%$

where 76.5% is the performance goal (PG).

The CFR at 12 months will be estimated using the Kaplan-Meier survival analysis. The associated one-sided lower 97.5% confidence interval will also be provided (using the Greenwood variance estimates). The null hypothesis is rejected at the 2.5% significance level if the LCB exceeds the PG of 76.5%. The p-value from the one-sided Z-test will be calculated and compared to the 2.5% significance level.

The primary analysis population for the primary safety endpoint analysis will be based on subjects in the full analysis population.

Statistical Analysis Plan

To eliminate the possible impact of Covid-19 on the confirmatory safety endpoint analysis, CEC adjudicated primary safety events (SADEs) that are related or possibly related to Covid-19 will be excluded from the primary safety endpoint analysis. Subjects who have these events will be censored at the time of the event. Additional analysis with these events included will also be provided.

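### The poolability check for the primary safety endpoint uses Fisher's exact test on a censored Kaplan-Meier outcome, and the visible text does not say how censored subjects are classified

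*SAP*

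**What the plan says.** SAP 2.9 sets the scope: "Poolability of the primary safety endpoint and the two primary effectiveness endpoints on subjects in the full analysis population will be evaluated by region". The same check is made by site. Region means US against outside the US; sites fall into three size categories. On data and method it says "Analysis will be performed based on available data" and "Consistency of results will be examined using Fisher's exact test and assessed at a significance level of 0.15". The text directly after that is redacted. No separate method for safety is visible.

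The safety endpoint is defined differently. SAP 2.3.1: "The CFR at 12 months will be estimated using the Kaplan-Meier survival analysis", with Greenwood variance. SAP 2.2.3: "Subjects without events will be censored at their last known event-free time point". SAP 2.3.1 also censors COVID-related safety events at the time of the event.

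Some early censoring is part of the design. For de novo subjects who leave the procedure with no device, Protocol 6.2.9 requires at least 30 days of follow-up, then: "At the end of the 30 days, the investigator will withdraw the subject". Protocol 6.4 does the same after all devices are removed or deactivated without replacement.

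**The concern.** Fisher's test needs a yes/no outcome for every subject in the table. A subject censored at day 40 has no 12-month outcome, so the analyst must either count that subject as event-free or drop the subject. The first choice understates risk where follow-up is shorter; the second overstates it, because event-free subjects are removed while subjects with events stay. Neither reproduces the Kaplan-Meier rate whose pooling is being justified. A subject with a COVID-related complication, censored in the primary analysis, would also need a rule.

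If follow-up differs between US and non-US subjects, the check could miss a real difference or signal one that does not exist, depending on a choice that is not visible in the plan.

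**Working it through.** The documents give no power or detectable difference for the poolability test, so there is no figure to reproduce. Its behaviour was simulated.

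**Inputs from the documents**
- Level 0.15 (SAP 2.9). Sidedness is not stated; two-sided is assumed.
- 300 de novo subjects for the primary endpoints (Protocol 5.6).
- Event timing: in a prior leadless study, all complications counted for the primary safety endpoint fell within 30 days (Protocol 4.1.1.1).
- 240 evaluable subjects for effectiveness endpoint #1 (Protocol 8.3). Against 300, that is (300 − 240)/300 = 20% not evaluable. This is only a rough guide to losses.

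**Assumptions, because no visible figure exists:** the regional split, the primary safety event rate, and the censoring rates and their difference by region.

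**Step 1. Size of the distortion.** Let r be the 12-month risk, c the share censored at about day 30, and L the share of events after day 30. With censored subjects counted as event-free, the table shows about r × (1 − c × L).
- L = 0.50: US 0.10 × (1 − 0.05 × 0.50) = 9.75%; non-US 0.18 × (1 − 0.20 × 0.50) = 16.2%. The true 8-point gap shrinks to 6.45.
- L = 0.05: US 0.10 × (1 − 0.0025) = 9.975%; non-US 0.18 × (1 − 0.01) = 17.82%. The gap is 7.845, almost intact.

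**Step 2. Detection of a regional difference.** 200 against 100 subjects, 10% against 18% risk, early censoring 5% against 20%; 2,000 to 3,000 trials per scenario, simulation error about 1 point. Pearson chi-square ignores censoring as Fisher does but lacks Fisher's discreteness, so it separates the two causes of loss.

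| Events by day 30 | Fisher, censored = event-free | Chi-square, same table | Log-rank |
|---|---|---|---|
| 50% | 54% | 56–57% | 66% |
| 95% | 66.5% | 67.9% | 68.8% |
| 100% | 67.3% | 69.0% | 69.2% |

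Over 90–100% early events, the range is about 64–67% for Fisher and 68–70% for log-rank. At 95% early events, discreteness explains 67.9 − 66.5 = 1.4 of the 68.8 − 66.5 = 2.3 points. At 50%, it explains only 2–3 of 12; the rest comes from ignoring unequal censoring.

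**Step 3. Equal censoring.** 150 against 150, 10% against 20% risk, early events. With no censoring, Fisher gives 79.8% and log-rank 84.0%; with 20% censoring in both groups, 80.5% and 84.8%. The gap is the same (4.2 and 4.3 points), so censoring is not its cause. Chi-square is within about 1 point of log-rank in every equal-censoring regional scenario.

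**Step 4. Site categories.** With 200/80/20 subjects, risks 10/20/20%, early events and 10% censoring, Fisher gives 76.3% and log-rank 75.7%. Across the site scenarios the two agree within about 2 points.

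**Step 5. Completers-only table.** With no true difference, 150 against 150, 10% risk, early events, and 5% against 30% censoring, nearly all of the 15 events per group are seen. Event-free completers are 135 × 0.95 = 128.25 and 135 × 0.70 = 94.5. The table then shows 15/143.25 = 10.5% against 15/109.5 = 13.7%, a spurious difference. In simulation (150:150 and 210:90 splits, 10% and 15% risk, 90% early events), this table rejects 21–26% of the time against the nominal 15%. Counting censored subjects as event-free rejects 12–13%. At 5% against 20% censoring, completers-only rejects about 17% in one run, and log-rank 15%.

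In the Step 2 alternatives the completers-only table flags 71–81%. That is not better power: the same distortion inflates the apparent difference.

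**The case against.** The strongest reply is that the protocol expects nearly all complications within 30 days. Subjects withdrawn at 30 days have then already passed the risk period, so counting them as event-free costs little. The 30-day withdrawal is also narrow: subjects who leave with one device are followed for at least 12 months (Protocol 6.2.8). No passage gives unequal censoring by region. Poolability is a supporting check that leaves the primary test unchanged; the 0.15 level is already lenient; descriptive summaries by region and site category are planned; and SAP 2.8 adds a tipping-point analysis for missing safety data. The redacted text after the quoted sentence may settle the classification.

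Most of this stands. It removes a stronger claim that a reader might infer: that ignoring censoring makes Fisher's test materially weaker at finding regional or site differences. Under the protocol's expected timing the regional gap is about 2–4 points, roughly half or more of it Fisher's own conservatism, and no meaningful loss is shown across site categories. The larger 54% against 66% contrast needs half the events to fall after day 30 and also unequal early censoring.

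The reply does not remove the mismatch between test and endpoint, or the fact that two readings of the visible text can behave very differently.

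**Conclusion.** The point holds in a limited form. The stated check tests a different quantity from the Kaplan-Meier rate it is meant to support, and its result depends on a classification that the visible text does not give.

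The power cost for region is about 2–4 points if 90–100% of events occur by day 30, and about 12 points if half do and early censoring is 5% against 20%. Across site categories there is no meaningful cost. The direction of error is not fixed: counting censored subjects as event-free makes the check somewhat conservative, while a completers-only table can give false signals of non-poolability (21–26% at 5% against 30% censoring with early events).

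All these sizes rest on assumed splits, risks and censoring rates. This is a desirable improvement and no threat to the primary conclusion. Confidence is moderate, because the adjoining text is redacted and may already deal with it.

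**What to change.** Amend SAP 2.9 so that, for the primary safety endpoint, US against non-US and the site categories are compared with a log-rank test at 0.15, or with a difference in 12-month Kaplan-Meier rates using Greenwood variance. Show 12-month Kaplan-Meier estimates with 95% confidence intervals for each stratum. Keep Fisher's exact test for the two binary effectiveness endpoints. If Fisher is retained for safety, state how subjects censored before 12 months, including those censored for COVID-related events, enter the table.

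The cost is one SAP sentence and minor programming, since Kaplan-Meier output is already planned for this endpoint. The one real downside is that the log-rank test is asymptotic and so less exact in small strata.

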2.10 Multiplicity Issues

[REDACTED]

Statistical Analysis Plan

2.11 Adjustments for Covariates

3.0 DESCRIPTIVE ENDPOINTS AND ADDITIONAL DATA

3.1 Baseline and Demographic Characteristics

The following baseline, demographic, medical history and medication variables will be summarized descriptively for the subjects in the enrolled population: gender, age, ethnicity, race, history of smoking; key cardiovascular history, prior cardiac interventions, arrhythmia history, primary indication for study device implant, use of beta blocker, ACE, ARB, anti-coagulation, anti-arrhythmic, and anti-platelet medications, etc. and as needed. For subjects enrolled from European sites, race and ethnicity may not be collected and hence data from some European countries may not be included in race/ethnicity summary of the demographics table.

3.2 Adverse Events

All reported adverse events (AE), serious adverse events (SAE), adverse device effects (ADE), serious adverse device effects (SADE), unanticipated adverse device effect (UADE) or unanticipated serious adverse device effect (USADE) will be summarized for all enrolled subjects using the number of events, the number of subjects with events and the percentage of subjects with events. All CEC adjudicated events will also be summarized for all enrolled subjects with the number of events, the number of subjects with events and the percentage of subjects with events. An AE listing which includes all adverse events and whether or not each event is device-related or procedure-related will be provided.

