This clinical investigation will enroll subjects of all genders over the age of 18 years who are indicated for a DDD(R) pacemaker. Patients must meet all general eligibility criteria and provide written informed consent prior to sites conducting any investigation-specific procedures not considered standard of care.

5.2 **Subject Recruitment/Screening and Informed Consent**

5.2.1 **Subject Recruitment and Screening**

The following assessments are performed as part of the subject recruitment process prior to obtaining informed consent:

- Demographics (age on consent date, gender)

Clinical Investigation Plan for Europe

- Medical history screening (including major cardiovascular, vascular, and other coexisting medical conditions associated with eligibility criteria)

A member of the site's clinical investigation team previously trained to the CIP must evaluate patients for the general clinical investigation eligibility criteria and will enter all screened patients into a site-specific recruitment/screening log. A patient who does not satisfy all general eligibility criteria prior to informed consent is considered a recruitment failure and should not be enrolled in the clinical investigation.

Sites will ask patients meeting general inclusion criteria and no general exclusion criteria to sign an Informed Consent form following the established Informed Consent process (described in Section 5.2.2) if they wish to participate in the clinical investigation. Sites will enter these patients into the recruitment/screening log.

Patients who have signed an informed consent and are subsequently found not to meet eligibility criteria prior to an attempted implant are considered screen failures and should be withdrawn.

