5.4 Subject Enrollment

A patient is considered enrolled in the clinical investigation from the moment the patient provides written informed consent.

All enrolled subjects who meet eligibility criteria should undergo an attempted implant. A subject may withdraw or be withdrawn prior to the implant attempt. If an enrolled subject does not undergo an attempted implant, the subject should be withdrawn as soon as possible.

If subjects receive a device without meeting all the conditions listed above, they should still complete all follow-up requirements. These subjects are considered CIP deviations.

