5.6 Number of Subjects

The clinical investigation will enroll up to 550 subjects at up to 85 sites worldwide to analyze the primary endpoints that is based on the following:

- 300 *de novo* subjects to evaluate the primary endpoints, including attrition
- Up to 200 *de novo* subjects [REDACTED]
- Up to 50 subjects to assess the upgradeability to a Aveir DR LP system in subjects previously implanted with the Aveir VR LP single chamber system

[REDACTED]

Subjects previously implanted with an Aveir VR LP who are enrolled to assess the upgradeability to an Aveir DR LP system (up to 50) will be concurrently enrolled with the *de novo* subjects but will not contribute toward the evaluation of the primary and secondary endpoints.

No site may enroll more than 15% of the total subjects required to evaluate the primary endpoints.

Clinical Investigation Plan for Europe

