2.1.1 Full Analysis Population

Full Analysis population includes all subjects who have an attempted implant. An implant is considered attempted when the Aveir Introducer Sheath or Aveir dilator is inserted through the skin of the access site.

[REDACTED]

[REDACTED]

Statistical Analysis Plan

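### SAP 3.2 puts device- and procedure-related event percentages on all consented subjects, so subjects who never reach an implant attempt dilute them slightly

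*SAP*

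**What the plan says.** SAP 3.2 covers AE, SAE, ADE, SADE, UADE and USADE in one sentence: they "will be summarized for all enrolled subjects using the number of events", together with how many subjects had events and what percentage that is. The next sentence extends this to adjudicated events: "All CEC adjudicated events will also be summarized for all enrolled subjects with the number of events".

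Protocol 5.4 defines the base: "A patient is considered enrolled in the clinical investigation from the moment the patient provides written informed consent". The same section adds: "A subject may withdraw or be withdrawn prior to the implant attempt". Protocol 5.2.1 says that patients who have consented and are "subsequently found not to meet eligibility criteria prior to an attempted implant are considered screen failures and should be withdrawn".

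The SAP already has an exposure-based population. In SAP 2.1.1, "Full Analysis population includes all subjects who have an attempted implant", and an attempt begins when the Aveir introducer sheath or dilator passes through the skin. SAP 2.3 and 2.3.1 use that population, restricted to de novo subjects, for the primary safety endpoint. SAP 2.3.4 does so for the secondary one.

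Protocol 5.6 allows up to 50 upgrade subjects, who "will not contribute toward the evaluation of the primary and secondary endpoints". They are nonetheless enrolled, so they fall within the SAP 3.2 summary. SAP 3.5 also plans a separate summary of upgrade-related adverse events.

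**The concern.** A subject who consents and is withdrawn before an implant attempt counts in the denominator but has no device and no implant procedure. That subject cannot add an adverse device effect to the numerator. The percentages for ADE, SADE, UADE/USADE and procedure-related events are therefore lower than the rates among exposed subjects, and the shift always favours the device.

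The study has a single arm, so no comparator carries the same dilution, and readers will take the absolute percentages at face value. The wider base also departs from the plan's own practice. Protocol Appendix II divides implant success by subjects in whom implantation was attempted, and upgrade success by subjects in whom an upgrade was attempted.

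A second, separate matter is that the table pools de novo and upgrade subjects, whose procedures differ: upgrade subjects already carry a ventricular LP and have an atrial LP added.

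**Working it through.** **Inputs from the documents**

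- Enrolment ceiling: 550 (Protocol 5.6, SAP 1.3).
- Components: 300 de novo for the primary endpoints, up to 200 more de novo, and up to 50 upgrades (Protocol 5.6, SAP 2.4). Check: 300 + 200 + 50 = 550, which reproduces the stated figure. Upgrades are 50/550 = 9.1% of the ceiling.
- The documents state no ADE or SADE rate for this table and no number of never-attempted subjects.

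**Assumptions**

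- f, the never-attempted share of enrolled subjects: 2%, 5% and 10%.
- p, the event rate among attempted subjects: 10% for illustration. This matches the 90% complication-free rate that Protocol 8.3 assumes for the secondary safety endpoint. Rates of 5% and 15% show the sensitivity.
- No never-attempted subject has a device- or procedure-related event.

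**Step 1: dilution from never-attempted subjects**

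Reported percentage = p × (1 - f).

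| f | Never attempted, of 550 | p = 5% | p = 10% | p = 15% |
|---|---|---|---|---|
| 2% | 11 | 4.90% | 9.8% | 14.70% |
| 5% | about 28 | 4.75% | 9.5% | 14.25% |
| 10% | 55 | 4.50% | 9.0% | 13.50% |

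For p = 10% the shortfall is 0.2 to 1.0 percentage points. In relative terms it always equals f, whatever the event rate.

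**Step 2: effect of pooling upgrade subjects**

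To isolate this, set f = 0 and the de novo rate at 10%. With upgrade rate u, the pooled rate = (500 × 10% + 50 × u) / 550.

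| u | Calculation | Pooled rate |
|---|---|---|
| 0% | 50.0/550 | 9.1% |
| 5% | 52.5/550 | 9.5% |
| 10% | 55.0/550 | 10.0% |
| 15% | 57.5/550 | 10.5% |
| 20% | 60.0/550 | 10.9% |

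The pooled rate falls below the de novo rate only if u is lower than 10%, and rises above it if u is higher. Unlike step 1, the direction is not fixed.

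**Step 3: reach**

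The primary and secondary safety endpoints are restricted to de novo subjects with an attempted implant (SAP 1.4, 2.3). Never-attempted and upgrade subjects do not enter them, so neither step alters those estimates or their tests against 76.5% and 82%.

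**The case against.** The best case for leaving the text alone has several parts.

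- **The share is probably small.** Under Protocol 5.2.1, general eligibility is checked before consent, and patients who fail at that stage are not enrolled. Protocol 5.4 expects eligible enrolled subjects to go on to an attempt. This stands, and it makes the lower end of the assumed range more plausible. Some loss must still be expected: Protocol 5.3.1 places non-standard screening tests after consent, and 6.1 does the same for any pregnancy test.
- **An all-enrolled base matches data collection.** Safety reporting starts at enrolment (Protocol 7.3.1). This stands for all-cause AE and SAE, where that base should remain.
- **Readers can re-divide.** Counts and an event listing with device and procedure relationship are planned. This is true, but it leaves the correction to the reader.
- **Some procedural events can precede the sheath.** Sedation or initial venous access may come before the defined start of an attempt, and sedation reactions and vascular puncture are foreseeable events in Protocol Appendix IV. This stands: the factor (1 - f) is exact only if such events do not occur in never-attempted subjects, and the fix must not lose them.
- **Redacted text may hold more.** Population text in SAP 2.1 and the whole of SAP 7.0 are blacked out, and an attempted-implant column or a split by subject type could sit there. This cannot be excluded, but the visible wording of SAP 3.2 is explicit about its population.

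A reader might also infer that including upgrade subjects pushes the rates down. The documents do not support that: these subjects undergo a procedure (Protocol 6.2.8), contribute events as well as person counts, and have their own summary in SAP 3.5. Nor would the fix make the table agree with the primary safety endpoint. That endpoint is a 12-month Kaplan-Meier estimate that censors Covid-19-related events, whereas the table is a crude percentage and adverse event reporting can continue past month 12.

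**Conclusion.** The point holds in a limited form. As worded, SAP 3.2 lowers device- and implant-procedure-related percentages by a relative amount equal to the never-attempted share. For an illustrative true rate of 10.0%, the reported figure would be 9.8% at f = 2% and 9.0% at f = 10%. The direction is clear under the stated assumption that unexposed subjects have no such events. The size rests on assumed values of f and is probably at the small end.

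Pooling upgrade subjects is a matter of interpretation, since it blends two procedures; it is not a source of systematic understatement. It would also be wrong to infer that the confirmatory safety conclusions are biased, because those analyses use attempted de novo implants. The point is minor: a cheap improvement to the descriptive tables.

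**What to change.** In SAP 3.2:

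1. Report percentages for ADE, SADE, UADE/USADE, procedure-related events and the device- or procedure-related subset of CEC-adjudicated events on subjects with an attempted implant or upgrade procedure.
2. Show de novo and upgrade subjects in separate columns, each with its own denominator.
3. Keep the all-enrolled summary for all-cause AE and SAE.
4. List events between consent and attempt separately, including any procedural event before sheath or dilator insertion, so that none disappears.
5. State the denominator in each table title, together with the number enrolled but never attempted.

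The cost is revised SAP wording and table shells. No new data are needed. The only downside for the sponsor is slightly higher reported rates.
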